3.9 Definition of an intercurrent event

Handling of intercurrent events is one of the key elements for the analysis of efficacy endpoints.

An intercurrent event is defined as receipt of systemic antibiotic rescue medication or discontinuation of study treatment due to an AE or lack of efficacy (See Section 8.2.2).

Receipt of systemic antibiotic rescue medication is defined as initiating any systemic antibiotic on or after Baseline for any reason (including in response to an AE). The only exception to this rule is if a participant randomized to the antibiotic stratum on a tetracycline antibiotic interrupts their stable dose of tetracycline antibiotic during the study and subsequently restarts the same tetracycline antibiotic as confirmed using the coded preferred term. The restarted dose and frequency of the antibiotic must be the same or lower than the regimen prior to the interruption.

The dates of an intercurrent event are as follows:

- For receipt of systemic antibiotic rescue medication: start date of the antibiotic
- For discontinuation of study treatment due to an AE or lack of efficacy: Last study treatment date + 17 days. Note: study treatment discontinuation includes study discontinuation.

The choice of 17 days is intended to capture the interval between dosing and lesion assessments (14 days), as well as the visit window (3 days).

An additional sensitivity analysis will be conducted where missing data due to COVID-19 will be considered an intercurrent event and will be imputed as a nonresponse at that particular visit. This will be identified when there are missing data at a visit that has been impacted by COVID-19 according the COVID-19 impact CRF page. The date of this intercurrent event will be the date of the impacted visit.

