4.2.1.1 Handling missing data for the primary efficacy endpoint

If study participants have an intercurrent event as defined in Section 3.9, then the primary efficacy variable at that timepoint and all subsequent timepoints (whether the data were observed or not) will be set to “nonresponse” as the study participant has not met the criteria for response based on the composite estimand defined in Section 8.2. All remaining missing data for the endpoint will be imputed using multiple imputation Markov-Chain Monte Carlo method (MI-MCMC)/monotone regression for the primary analysis.

In addition, sensitivity analyses using NRI, MI-MCMC/reference-based methods, tipping point analysis, and observed case (OC) methods will be performed, which will assess the impact of different methods of handling missing data.

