Objective Clinical Category	Statistical Category (Section)	Estimands for Primary Endpoint			
		Variable/ Endpoint	Pop	IES	PLS (Analysis)
HiSCR ₅₀	Sensitivity (Section 8.2.3.9)	HiSCR ₅₀ response at Week 16	RS	The same two intercurrent events used for the primary analysis will be used. Any missing data due to COVID-19 will also be considered an intercurrent event. A composite strategy will be used, ie, the occurrence of an intercurrent event will be handled by evaluating the corresponding participants as treatment failures (nonresponders).	The odds ratio versus placebo is based on a logistic regression, as for the primary analysis.
HiSCR ₅₀	Sensitivity (Section 8.2.3.10)	HiSCR ₅₀ response at Week 16	RS	Composite strategy , as for the primary analysis.	The odds ratio versus placebo based on a stratified Cochran-Mantel-Haenszel (CMH) test. Missing values not preceded by an intercurrent event will be imputed using MI – MCMC/Monotone Regression under a missing at random assumption.

CFS=Covid-19 Free Set; CMH=Cochran-Mantel-Haenszel; COVID-19=coronavirus disease 2019; FAS=Full Analysis Set; HiSCR=Hidradenitis Suppurativa Clinical Response; IES=intercurrent event(s) strategy; MCMC=Markov Chain Monte Carlo; MI= multiple imputation; PLS=Population-level summary; Pop=Population; PPS=Per-Protocol Set; RS=Randomized Set

^aThe composite estimand strategy will be modified in the tipping point analysis such that participants with intercurrent events will be treated as nonresponders only in the bimekizumab treatment groups.

8.2.1 Derivation of HiSCR₅₀ at Week 16

The following algorithm will be applied to derive HiSCR₅₀ at each visit, based on total lesion counts across anatomical regions for the 3 relevant lesion types recorded as specified above in Section 8.1:

1. Calculate the AN count at each visit as the total number of abscesses plus the total number of inflammatory nodules, across all anatomical regions
2. Calculate the percentage change from Baseline in AN count (%ΔAN) at each visit as

$$100 \times \frac{(AN \text{ count at post-Baseline visit} - \text{Baseline AN count})}{(\text{Baseline AN count})}$$

3. Calculate the change from Baseline in the abscess count by subtracting the Baseline abscess count from the abscess count at each post-Baseline visit

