8.2.3.9 Analysis including COVID-19 impact as intercurrent event

An additional sensitivity analysis will include an additional intercurrent event. The composite estimand combines the clinically meaningful improvement from Baseline based on the HiSCR₅₀ response and completion of study treatment through Week 16 without receiving systemic antibiotic rescue medication or discontinuing IMP due to an AE or lack of efficacy.

The following 4 attributes describe the estimand that will be used to define the treatment effect of interest for this sensitivity efficacy analysis:

1. Population=Study participants meeting the protocol-specified inclusion/exclusion criteria.
2. Study participant-level outcome=HiSCR₅₀ at Week 16.
3. Intercurrent event handling=An intercurrent event is defined as receipt of systemic antibiotic rescue medication, discontinuation of study treatment due to an AE or lack of efficacy prior to Week 16, or missing data due to COVID-19. More information is provided in Section 3.9. A composite strategy will be implemented in which a positive clinical outcome is defined as achieving HiSCR₅₀ at Week 16 and not receiving systemic antibiotic rescue medication, not discontinuing study treatment due to an AE or lack of efficacy through Week 16, and not having missing data due to COVID-19. Any missing data at Week 16 that are not preceded by an intercurrent event will be imputed using multiple imputation as defined in Section 4.2.1.
4. Population-level summary measure=conditional odds ratio comparing bimekizumab to placebo adjusted for stratification factors used in the randomization.

The same imputation techniques and analysis model as in the primary efficacy analyses will then be used.

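### The COVID-19 sensitivity analysis of HiSCR50 is scored per visit in SAP Section 3.9 but per participant in Table 8-1 and Section 8.2.3.9, so some observed Week 16 responders count as responders under one and failures under the other.

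*SAP*

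**What the plan says.** Four places in the current SAP text bear on how a COVID-19-missed visit is scored.

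- **Section 3.9** introduces the sensitivity analysis and states that missing data due to COVID-19 "will be imputed as a nonresponse at that particular visit". The visit is identified from the COVID-19 impact CRF page, and "The date of this intercurrent event will be the date of the impacted visit".
- **Table 8-1, row for Section 8.2.3.9**, states: "Any missing data due to COVID-19 will also be considered an intercurrent event". It then says that "the occurrence of an intercurrent event will be handled by evaluating the corresponding participants as treatment failures (nonresponders". The unit that fails is the participant, and no visit is named.
- **Section 8.2.3.9** defines a positive outcome as HiSCR50 at Week 16 without rescue antibiotics, without discontinuation for an AE or lack of efficacy, "and not having missing data due to COVID-19". It sends to multiple imputation only those missing Week 16 values that have no earlier intercurrent event. It refers to Section 3.9 for detail, and also says that the primary-analysis imputation techniques and model are used.
- **Section 4.2.1.1**, on the primary endpoint, relies on Section 3.9 for what counts as an event and carries the score forward: "then the primary efficacy variable at that timepoint and all subsequent timepoints (whether the data were observed or not) will be set to “nonresponse".

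**The concern.** This analysis should show how far COVID-19 missing data could change the Week 16 result. It can do so only if the scoring rule is unambiguous. As written, two programmers following the SAP could build different Week 16 datasets.

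Under the participant-level wording, an observed Week 16 response is overwritten because an earlier visit was missed for a reason that need not relate to treatment or outcome. Response rates then fall in both arms and the odds ratio moves towards 1. Part of any weakening of the effect would come from the rule and not from Week 16 data lost to the pandemic.

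**Working it through.** **Step 1. Apply the wordings to single participants.** In each case there is no rescue antibiotic and no discontinuation.

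| Participant | Section 3.9 | Table 8-1 and Section 8.2.3.9 as written |
|---|---|---|
| A: Week 8 missed due to COVID-19; Week 16 observed, HiSCR50 met | Responder | Failure |
| B: Week 8 missed due to COVID-19; Week 16 missing for another reason | Multiply imputed | Failure |
| C: Week 16 itself missed due to COVID-19 | Failure | Failure |

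Participants A and B are scored differently; C is not. If the carry-forward in Section 4.2.1.1 were applied to the COVID-19 event, A would also be a failure at Week 16. There are therefore several wordings but only two Week 16 outcomes.

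The cross-references do not settle the matter. Section 8.2.3.9 points to Section 3.9 (visit only) and also to the primary-analysis imputation techniques, which lead to Section 4.2.1.1 (carry forward). Dating the event to the missed visit, as Section 3.9 does, allows an earlier miss to count as preceding Week 16.

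**Step 2. Reproduce the plan's power.** Inputs from SAP Section 2.4 and Table 2-1: HiSCR50 rates 0.60 (Q2W, n = 280), 0.50 (Q4W, n = 140) and 0.25 (placebo, n = 70); two-sided alpha 0.025, so z = 2.2414. The pooled-variance normal approximation is

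power = Φ{(p2 − p1 − z·se0)/se1},

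with se0 = √[p̄(1 − p̄)(1/n1 + 1/n2)] and se1 = √[p1(1 − p1)/n1 + p2(1 − p2)/n2].

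For Q4W versus placebo:

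- p̄ = (17.5 + 70)/210 = 0.4167
- se0 = 0.0722 and se1 = 0.0668
- power = Φ{(0.25 − 2.2414 × 0.0722)/0.0668} = Φ(1.32) = 0.907, against 0.90 stated

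For Q2W the result is 0.9996, against 0.99 stated. Both agree with the plan.

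**Step 3. Size of the disputed difference.** Let c be the share of each arm whose only COVID-19-missed visits fall before Week 16. Assume c is equal across arms and independent of response, and take the planned rates as those obtained under Section 3.9. The SAP gives no value for c. Under the participant-level wording each rate becomes p(1 − c), and OR = [p2/(1 − p2)]/[p1/(1 − p1)].

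| c | Q4W rate | Placebo rate | OR | Q4W power | Q2W power |
|---|---|---|---|---|---|
| 0 | 0.500 | 0.250 | 3.00 | 0.907 | 0.9996 |
| 2% | 0.490 | 0.245 | 2.96 | 0.896 | 0.9995 |
| 5% | 0.475 | 0.2375 | 2.90 | 0.878 | 0.9991 |
| 10% | 0.450 | 0.225 | 2.82 | 0.845 | 0.998 |
| 20% | 0.400 | 0.200 | 2.67 | 0.763 | 0.990 |

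Example at c = 5%: (0.475/0.525)/(0.2375/0.7625) = 0.9048/0.3115 = 2.90.

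**The case against.** A reader might infer three competing scoring rules, with Section 4.2.1.1 in direct conflict with Section 3.9. The documents do not support that. Section 4.2.1.1 concerns the primary analysis, and the defining sentence of Section 3.9, like Section 4.2.1, names only two events: rescue antibiotics, and discontinuation for an AE or lack of efficacy. COVID-19 enters Section 3.9 later, as an additional sensitivity analysis with its own scoring. Section 4.2.1.1 therefore competes only indirectly, through the reference in Section 8.2.3.9 to the primary-analysis imputation techniques. Those words may mean no more than multiple imputation followed by logistic regression.

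It can also be argued that Section 8.2.3.9 agrees with Section 3.9. The outcome is HiSCR50 at Week 16, so the COVID-19 condition could mean missing Week 16 data. That reading is possible, but neither Section 8.2.3.9 nor Table 8-1 states it. The table refers to any missing data and fails the participant. That Section 3.9 is the more specific text does not decide it either, because all three places are specific to this one analysis.

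A reader might also apply the power loss to everyone with a COVID-19-missed visit up to Week 16. That is too broad: those whose Week 16 visit was itself missed for COVID-19 are nonresponders under every reading.

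Finally, this analysis lies outside the testing sequence of Section 4.5. The COVID-19 Free Set analysis and the nonresponse-imputation analysis give context for any weakened result. This stands, and it limits the weight of the point.

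**Conclusion.** The inconsistency is real and lies in current text. Section 3.9 scores the missed visit; Table 8-1 and Section 8.2.3.9, as written, fail the participant. Two groups are scored differently: those with an earlier COVID-19 miss and an observed Week 16 response, and those with an earlier COVID-19 miss whose Week 16 value is missing for another reason.

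The severity is minor. One sensitivity analysis is affected; the primary test, alpha and sample size are not. The sizes in the table are illustrative and rest on an assumed share of earlier-only misses, equal across arms and independent of response. On that basis the Q4W odds ratio stays at about 2.67 or above for shares up to 20%. The power figures describe how often this supportive result would reach significance at 0.025; no confirmatory claim depends on them.

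**What to change.** In Section 8.2.3.9 and the matching row of Table 8-1, state that the COVID-19 event is a missing Week 16 lesion assessment at a visit flagged on the COVID-19 impact CRF page, scored as nonresponse at Week 16 only. This follows Section 3.9 and keeps observed Week 16 data.

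In Sections 4.2.1.1 and 8.2.3.9, state that the carry-forward to later timepoints, and the exclusion from multiple imputation because of an earlier intercurrent event, apply only to rescue antibiotics and to discontinuation for an AE or lack of efficacy. The opening paragraph of Section 8.2.3.9 restates the composite without the COVID-19 condition and should be aligned at the same time.

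The cost is a few sentences of SAP wording, with no new data and no change to the primary analysis.

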3.10 Changes to protocol-defined analyses

The MS and AMS were added as analysis sets.

The endpoints for PGI-S-HS, PGI-S-SP, PGI-C-HS, and PGI-C-SP were clarified in Section 2.2.1.3 to indicate that absolute change from Baseline will not be calculated, as these are categorical endpoints.

The HiSQOL endpoint was clarified to show that there are only 3 domains: symptoms, psychosocial, activities and adaptations and to add total score.

In Protocol Amendment 4, the secondary efficacy endpoint for skin pain response based on the worst skin pain HSSDD score is defined as a decrease from Baseline in HSSDD weekly worst skin pain score at or beyond the threshold for clinically meaningful change at Week 16. In the HS0003 SAP, this endpoint is defined to include the exact value of the clinically meaningful threshold of 3, so that the skin pain response based on the HSSDD worst skin pain score is defined as at least a 3 point decrease from Baseline in HSSDD weekly worst skin pain score at Week 16 among study participants with a score of ≥ 3 at Baseline.

The following other efficacy endpoints are included in the protocol but will not be included as part of the analysis:

- Skin pain response based on the threshold for clinically meaningful change (defined as at least a 3 point decrease from Baseline in HS Symptom Questionnaire (HSSQ) weekly worst skin pain score) among study participants with a score of ≥ 3 at Baseline
- Response on other HS Symptoms (11-point numeric rating scale) - itch, drainage or oozing of HS lesions, and smell or odor
- Flare (defined as a $\geq 25\%$ increase in AN count with an absolute increase in AN count of ≥ 2 relative to Week 16) by Week 48

The calculation of nominal p-values has been added for selected efficacy endpoints. These nominal p-values are not controlled for multiplicity and should not be used to declare statistical significance.

The protocol defines the PK-PPS separately by period, but there will only be one PK-PPS for the overall study.

4 STATISTICAL/ANALYTICAL ISSUES

4.1 Adjustments for covariates

The primary efficacy analyses and selected secondary analyses will be adjusted for the 2 randomization stratification variables:

- Hurley Stage at Baseline (II or III)
- Baseline antibiotic use (Yes or No)

If a participant is stratified in the incorrect stratum (ie, the stratum recorded in the Interactive voice or web Response System differs from the actual stratum the participant belongs to), the actual stratum will be used for the analysis.

The continuous secondary endpoints will also include the Baseline value as a covariate.

The Worst Skin Pain secondary endpoints (change from Baseline continuous endpoint and pain response binary endpoint) will also include analgesic use as a covariate.

4.2 Handling of dropouts or missing data

4.2.1 Efficacy data

Different approaches will be used to handle missing data including how intercurrent events (defined as receipt of systemic antibiotic rescue medication or discontinuation of study treatment due to an AE or lack of efficacy prior to the given visit) will be considered. A composite strategy will be implemented in which a positive clinical outcome is defined as the study participant achieving HiSCR₅₀ at the given visit and not receiving systemic antibiotic rescue medication, and not discontinuing study treatment due to an AE or lack of efficacy through that visit.

4.2.1.1 Handling missing data for the primary efficacy endpoint

If study participants have an intercurrent event as defined in Section 3.9, then the primary efficacy variable at that timepoint and all subsequent timepoints (whether the data were observed or not) will be set to “nonresponse” as the study participant has not met the criteria for response based on the composite estimand defined in Section 8.2. All remaining missing data for the endpoint will be imputed using multiple imputation Markov-Chain Monte Carlo method (MI-MCMC)/monotone regression for the primary analysis.

In addition, sensitivity analyses using NRI, MI-MCMC/reference-based methods, tipping point analysis, and observed case (OC) methods will be performed, which will assess the impact of different methods of handling missing data.

4.2.1.2 Handling missing data for the secondary efficacy endpoints

For secondary binary efficacy endpoints, intercurrent events will be handled, and missing data will be imputed, using the same methods as for the primary efficacy endpoint. NRI and OC methods will be performed as sensitivity analyses.

For secondary continuous efficacy endpoints, MI-MCMC/monotone regression is the primary method for imputing missing data, regardless of whether the missing data are preceded by an intercurrent event. That is, if an intercurrent event occurs on or before a visit, the result for that visit will be treated as missing and then imputed. If the imputation model cannot converge, last observation carried forward (LOCF) will be used. The OC method will be performed as a sensitivity analysis.

4.2.1.3 Handling missing data for the other efficacy endpoints

For other binary efficacy endpoints, missing data will be imputed using the same method as the primary efficacy endpoint. NRI and OC methods will be performed as sensitivity analyses of HiSCR₅₀, HiSCR₇₅, HiSCR₉₀, and HiSCR₁₀₀.

For other continuous efficacy endpoints, the MI-MCMC/monotone regression method will be used to impute missing data as the primary method, regardless of whether the missing data are preceded by an intercurrent event. That is, if an intercurrent event occurs on or before a visit, the result for that visit will be treated as missing and imputed with the missing data. If the imputation model cannot converge, LOCF will be used.

For other ordinal endpoints (EQ-5D-3L, PGI-S-HS, PGI-C-HS, PGI-S-SP, PGI-C-SP), the OC method will be applied as the primary analysis method. No imputation is applied.

4.2.1.4 Missing Data Overview and Summary

In summary, the approaches listed below will be used in this study for handling missing data for efficacy endpoints as appropriate:

- **NRI:** Participants who have missing data at the timepoint of interest are treated as though they did not respond to the treatment. This approach is also referred to as Composite Estimand (NRI).
- **Multiple Imputation (MI) – MCMC / Monotone Regression:** Using multiple imputation methodology, intermittent missing data are imputed based on the MCMC method, and monotone missing data are imputed using monotone regression.
- **MI–MCMC / Reference-based imputation:** Using multiple imputation methodology, intermittent missing data are imputed based on the MCMC method, and monotone missing data are imputed using an imputation model based on placebo (reference) data.
- **LOCF:** Post-Baseline missing data are imputed by carrying forward the last available observation (including Baseline).
- **Tipping point analyses:** Assumptions will be made about average outcomes among the subsets of participants who prematurely discontinued study treatment. Various “delta adjustments” will be made to the assumed responses among missing data in each treatment arm with varying degrees of plausibility in order to identify assumptions about the missing data under which the conclusions change (O’Kelly, 2014). Then, the plausibility of such assumptions is discussed.
- **Observed case (OC):** Missing data are not imputed. Only participants with available data who have not discontinued study treatment at the given timepoint are considered. Study participants with missing data or who have prematurely discontinued study treatment will be treated as missing.
- **Treatment policy strategy:** All available data observed at the time point of interest will be considered, regardless of the occurrence of intercurrent events. This means the analysis includes on- and off-treatment values collected after study participants prematurely discontinued study treatment but agreed to remain on the study and continued to attend visits and provide assessments at those visits as well as values from study participants who received rescue antibiotic medication. Those observed values will be analyzed according to the study participant’s randomized treatment. Study participants for whom efficacy data cannot be obtained at the week of interest, despite attempts to retain them in the study, will have their data imputed using MI – MCMC / monotone.

The following table depicts which missing data handling approaches will be used based on endpoint priority (primary, secondary, other) and endpoint type (responder, continuous, ordinal).

Table 4–1: Missing data handling approach by endpoint priority and type

End-point Priority	Endpoint Type	Composite Estimand (NRI)	Modified Composite Estimand (MI)	MI (MCMC/Reference -based)	Tipping Point	Treatment Policy	Hypothetical Estimand	OC
Primary	Responder	S ^a	P	S ^a	S	S ^a		S
Secondary included in the statistical testing procedure	Responder	S ^a	P					S
	Continuous						P	S
Secondary not included in statistical testing procedure	Binary	X	X					X
	Continuous						X	X
Other	Responder	X ^d	X					X ^d
	Continuous						X	X ^b
	Ordinal						X ^c	X ^c

MI=multiple imputation, NRI=Nonresponder imputation, OC=Observed case, P=Primary method, S=Sensitivity method, X=Method to be used (no priority designated).

Note: Composite estimand (NRI) refers to the approach in which data preceded by the intercurrent event of study treatment discontinuation due to AE or lack of efficacy or receipt of rescue antibiotic medication are imputed as nonresponse, and other missing data are also imputed as nonresponse.

Note: Modified Composite Estimand (MI) refers to the approach in which data preceded by the intercurrent event of study treatment discontinuation due to AE or lack of efficacy or receipt of rescue antibiotic medication are imputed as nonresponse, and other missing data are imputed via a multiple imputation model.

Note: Hypothetical Estimand (MI) refers to the approach where outcomes for study participants without an intercurrent event of study treatment discontinuation are as observed, and outcomes for study participants with the intercurrent event are imputed via a multiple imputation model.

^a Imputation method is applied on continuous data, and responder endpoint is derived from the continuous endpoint based on complete data set where applicable.

^b Required only for by-visit summaries of variables whose value at Week 16 is part of the hierarchical testing procedure.

^c For variables with multiple categories, data will be summarized as observed with an additional missing row to capture missing data at a given visit.

^d NRI/OC sensitivity analysis will be performed only for HiSCR₅₀, HiSCR₇₅, HiSCR₉₀, HiSCR₁₀₀ summaries.

